## **Appendix II. Skin Type – Oiliness Level**

At Screening (Visit 1), subjects will rate their self-perceived skin type in terms of oiliness as per the scale below:

[figure not shown]
How would you classify your facial skin?

- Oily
- Dry
- Normal
- Combination

[figure not shown]
This is for demographic information collection purposes only and is not considered an evaluation endpoint.

### Appendix III. Ingredient Lists

#### AM & PM Cleanser,

#### AM Moisturizer (with SPF 30),

**Appendix IV. Clinical and Subjective Evaluations of Efficacy [REDACTED] – Grading Scales**

**A) Efficacy:** To be independently evaluated by the PI and 2 other Expert Graders (note: only the PI will evaluate the subject at Screening [Visit 1]).

1) Each subject’s face will be evaluated for the following efficacy parameters using the **Fitzpatrick Wrinkle and Elastosis Scale** shown below. One score will be assigned by each grader for each parameter. Half points are allowed.

- Fine lines
- Periorbital wrinkles
- Global wrinkling

**Fitzpatrick Wrinkle and Elastosis Scale:**

Class	Score	Wrinkling	Degree of Elastosis
I	1-3	Fine wrinkles	Mild (fine textural changes with subtle skin lines)
II	4-6	Fine to moderate depth, moderate number of lines	Moderate (distinct papular elastosis, individual papules with yellow translucency, dyschromia)
III	7-9	Fine to deep wrinkles, numerous lines, with or without redundant skin	Severe (multipapular and confluent elastosis, thickened yellow and pallid cutis rhomboidalis)

2) Each subject’s face will be evaluated for the following efficacy parameters using the **Modified Griffiths Scale** shown below. One score will be assigned by each grader for each parameter. Half points are allowed.

- Surface roughness – this factor represents a combined assessment of the appearance and feel of the skin’s roughness.
- Uneven skin tone
- Mottled hyperpigmentation – this factor represents a visual assessment of light, patchy, mottled hyperpigmentation and solar freckling (including melasma) based on quantitative and qualitative criteria such as the area/density of pigment, color intensity (dark vs. light), and uniformity of distribution (i.e., the more uneven or blotchy, the greater the score). Lentigines, nevi, and other pigmented lesions are not to be included in this assessment.
- Sallowness or yellowing – this factor represents a visual assessment of color tone from no yellow undertones to very sallow or pronounced yellow undertones.
- Lack of radiance

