#### 4.2.1. Inclusion Criteria

- a) Has read, understood, signed, dated, and received a copy of the Photograph Release and ICD (including a Health Insurance Portability and Accountability Act [HIPAA] disclosure) after the nature of the study has been fully explained.
- b) Female
- c) 35 to 70 years old
- d) Has clinically determined mild to moderate mottled hyperpigmentation on the face at Visit 1, defined as a score of 1-6 on the 10-point Modified Griffiths Scale (see section 7.2.3.3.1), as determined by the PI.
- e) Has clinically determined moderate to severe global facial wrinkling at Visit 1, defined as a score of 4-9 on the 9-point Fitzpatrick Wrinkle and Elastosis Scale (see section 7.2.3.3.1), as determined by the PI.
- f) Fitzpatrick Skin Type I, II, III, IV, V, or VI (an approximately equal number of subjects will be enrolled per skin type per cell; Appendix I).
- g) Able to read, write, speak, and understand English.
- h) Generally in good health based on medical history reported by the subject, as determined by the PI or designee.
- i) Intends to complete the study and is willing and able to fulfill the subject responsibilities (see section 4.2.3).
- j) Meets one of the following criteria:
  - Is not of child-bearing potential or is in a monogamous relationship with a partner who is not of child-bearing potential, meaning the subject and/or partner:
    - Is post-menopausal (amenorrhea for at least 1 year)
    - Had a surgical sterilization (e.g., vasectomy that has been confirmed effective by sperm count check, tubal occlusion, hysterectomy, bilateral oophorectomy or salpingectomy)
  - Must agree to practice a medically acceptable form of birth control during the study and for 30 days after study completion. Female subjects must have used such birth control for at least 3 months prior to study start. Medically acceptable forms of birth control that may be used by the subject and/or partner include:
    - Established use of hormonal methods of contraception (oral, injected, implanted, hormone patch or vaginal ring)
    - Barrier methods of contraception: condom or occlusive cap (diaphragm or cervical/vault caps)
    - Intrauterine device or intrauterine system
    - Abstinence from intercourse that could cause pregnancy. Periodic abstinence (e.g., calendar, ovulation, symptothermal, post-ovulation methods) and withdrawal are not acceptable methods of contraception.

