### **8.2.2. Analysis of Secondary Variables**

The secondary efficacy variables are the change from baseline in the following endpoints at Week 1, Week 4, Week 12, and Week 24. Scores from the 3 Expert Graders will be averaged for the baseline as well as each post-baseline visit before computing the change.

- Global wrinkling (excluding Week 12, the primary time point)
- Fine lines
- Periorbital wrinkles
- Surface roughness
- Uneven skin tone
- Mottled hyperpigmentation
- Sallowness or yellowing
- Lack of radiance

The active mask will be compared with the sham mask. Treatment means and between-treatment differences will be assessed by means of an ANCOVA model with treatment and skin type group as factors and the corresponding averaged baseline score as a covariate. The two-sided 95% confidence interval for the treatment difference will be presented.

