**Mottled Hyperpigmentation (using Modified Griffiths Scale):**

[figure not shown]
Rating (Score)	Category	Description
0	None	Perfectly even in tone (no redness or hyperpigmentation).
1-3	Mild	Early color variation; no lentigines (freckles may be present).
4-6	Moderate	Early to moderate dyspigmentation/telangiectasia may be present; one or more lentigines.
7-9	Severe	Dyschromia (mottled and/or discrete) is likely, or it may be replaced by quite definite yellowing.

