4 ENDPOINTS AND COVARIATES

A) Efficacy: To be independently evaluated by the Principal Investigator (PI) and 2 other Expert Graders (note: only the PI will evaluate the subject at Screening [Visit 1]).

Fitzpatrick Wrinkle and Elastosis Scale

Fine lines, Periorbital wrinkles and Global wrinkling will be evaluated using the Fitzpatrick Wrinkle and Elastosis Scale. Half points are allowed:

Class	Score	Wrinkling	Degree of Elastosis
I	1-3	Fine wrinkles	Mild (fine textural changes with subtle skin lines)
II	4-6	Fine to moderate depth, moderate number of lines	Moderate (distinct papular elastosis, individual papules with yellow translucency, dyschromia)
III	7-9	Fine to deep wrinkles, numerous lines, with or without redundant skin	Severe (multipapular and confluent elastosis, thickened yellow and pallid cutis rhomboidalis)

Modified Griffiths Scale

Surface Roughness, Uneven Skin Tone, Mottled Hyperpigmentation, Sallowiness or Yellowing, Lack of Radiance [REDACTED] will be evaluated using the Modified Griffiths Scale. Half points are allowed:

Rating (Score)	Category	Description
0	None	See below for parameter-specific descriptions.
1-3	Mild	
4-6	Moderate	
7-9	Severe	

Surface Roughness (using Modified Griffiths Scale):

Rating (Score)	Category	Description
0	None	Skin perfectly smooth.
1-3	Mild	Slight laxity of skin. Some surface roughness visible.
4-6	Moderate	Tactile and/or visible roughness demonstrable.
7-9	Severe	Topography of skin (visible and tactile) is undulating and rough.

Uneven Skin Tone (using Modified Griffiths Scale):

Rating (Score)	Category	Description
0	None	Uniform natural skin color; perfect evenness.
1-3	Mild	“Barely” to “slightly” to “slightly to mildly”...perceivable areas of redness, yellowness, or darkness.
4-6	Moderate	“Mildly to moderately” to “moderately” to “pronounced”...perceivable areas of redness, yellowness, or darkness.
7-9	Severe	“Pronounced” to “pronounced to significantly” to pronounced (severe)”... perceivable areas of redness, yellowness, or darkness.

Mottled Hyperpigmentation (using Modified Griffiths Scale):

[figure not shown]
Rating (Score)	Category	Description
0	None	Perfectly even in tone (no redness or hyperpigmentation).
1-3	Mild	Early color variation; no lentigines (freckles may be present).
4-6	Moderate	Early to moderate dyspigmentation/telangiectasia may be present; one or more lentigines.
7-9	Severe	Dyschromia (mottled and/or discrete) is likely, or it may be replaced by quite definite yellowing.

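### Mottled hyperpigmentation is defined to exclude lentigines, yet its scale anchors use lentigines to separate mild from moderate, so on faces with persisting lentigines some graders can score below 4 and others cannot

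*Protocol*

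**What the plan says.** Protocol Appendix IV, part A, item 2, describes what is to be scored: "this factor represents a visual assessment of light, patchy, mottled hyperpigmentation and solar freckling (including melasma", judged on how much pigment there is, how dark it is and how evenly it is spread. It then closes the definition with an exclusion: "Lentigines, nevi, and other pigmented lesions are not to be included in this assessment".

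The scale table for the same parameter, later in Appendix IV, describes the mild band (1-3) as "Early color variation; no lentigines (freckles may be present" and the moderate band (4-6) as "Early to moderate dyspigmentation/telangiectasia may be present; one or more lentigines". SAP section 4 reproduces both anchors without the exclusion sentence.

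The score is used in two places:

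- **Entry.** Inclusion criterion d in Protocol section 4.2.1 requires mild to moderate mottled hyperpigmentation, "defined as a score of 1-6 on the 10-point Modified Griffiths Scale", as judged by the principal investigator at Visit 1.
- **Efficacy.** It is one of the secondary variables in Protocol section 8.2.2: "The secondary efficacy variables are the change from baseline in the following endpoints at Week 1, Week 4, Week 12, and Week 24". Three graders score independently ("One score will be assigned by each grader for each parameter. Half points are allowed"), and then "Scores from the 3 Expert Graders will be averaged for the baseline as well as each post-baseline visit before computing the change".

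SAP section 6.4.2 bases the secondary analyses on average scores. It specifies separate per-grader analyses for the primary variable, global wrinkling.

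**The concern.** A grader cannot both leave lentigines out of the assessment and use their presence or absence to choose the band. Two competent graders looking at the same face could each cite Appendix IV and land on opposite sides of the 3/4 boundary.

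A difference in level between graders matters little if each keeps to one rule, because it largely drops out of the change from baseline. What does not drop out is the floor. If a face has lentigines that do not clear, an anchor-following grader has no route below 4, however much the mottling improves. That shrinks recorded improvement in whichever arm improves, and so pulls the active-sham difference on this endpoint towards zero. Because the planned analysis uses only the three-grader average, a split in rules would not appear in the reported results.

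**Working it through.** **Step 1: the texts side by side.** The plan gives no figure on this point, so there is none to reproduce. Take a face whose mottling alone merits a 3 and which also has one lentigo.

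- Definition (Appendix IV, item 2): lentigines do not count, so the score is 3.
- Anchors (Appendix IV table; SAP section 4): the mild band requires no lentigines and the moderate band names one or more, so the lowest matching score is 4.

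Both readings can be defended from the page. The bands also differ in degree of pigment change, but lentigines are the only present/absent feature that separates them.

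**Step 2: one face.** Assume the lentigines persist. A definition-following grader records s, and an anchor-following grader records max(s, 4). With k of 3 graders following the anchors, baseline b of at least 4 and true fall d:

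recorded mean fall = b − [k × max(b − d, 4) + (3 − k) × (b − d)] / 3

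For d = 1.0:

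| Baseline | k = 0 | k = 1 | k = 2 | k = 3 |
|---|---|---|---|---|
| 4 (formula reduces to 1 − k/3) | 1.00 | 0.67 | 0.33 | 0 |
| 4.5 (reduces to 1 − k/6) | 1.00 | 0.83 | 0.67 | 0.50 |
| 5 or 6 | 1.00 | 1.00 | 1.00 | 1.00 |

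The loss runs from none to complete, depending on the baseline score and on how many graders follow the anchors.

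**Step 3: a group of women.** All inputs here are assumptions: baselines spread evenly over the nine half-point values from 2.0 to 6.0, a true fall of 1.0 in every woman, and persisting lentigines in a share p of 25%, 50% or 75%.

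On faces with lentigines, an anchor-following grader records a fall of 0 at the five baselines from 2 to 4, 0.5 at 4.5, and 1.0 at 5, 5.5 and 6. The mean is (0.5 + 3 × 1.0) / 9 = 3.5/9 = 0.39, a loss of 5.5/9 = 0.611 against the true 1.0.

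Three-grader mean fall = 1 − (k/3) × p × 0.611

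| Graders following the anchors | p = 25% | p = 50% | p = 75% |
|---|---|---|---|
| 1 of 3 | 0.95 | 0.90 | 0.85 |
| 2 of 3 | 0.90 | 0.80 | 0.69 |
| 3 of 3 | 0.85 | 0.69 | 0.54 |

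**Step 4: the level gap at baseline.** On faces with lentigines, an anchor-following grader scores higher by 2, 1.5, 1 and 0.5 at baselines 2, 2.5, 3 and 3.5, and by nothing above that: 5/9 = 0.556 on average. Over all women the gap between the two kinds of grader is p × 0.556 = 0.14, 0.28 or 0.42.

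**A limit of the model.** Half points are allowed, and 3.5 lies between the printed bands. The model treats it as closed to an anchor-following grader. If such a grader would use 3.5, the floor moves down half a point and the losses are smaller.

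**The case against.** The strongest reply is that the conflict is less open than it looks. The exclusion is a direct instruction specific to this parameter, whereas the anchors are band descriptions. The moderate anchor for sallowness also mentions lentigines, although they are not yellowing, which suggests an accompanying descriptor and not a gate. The graders are dermatologists and may simply obey the exclusion. This is reasonable, and it may be how most graders would behave. But the plan does not say so, and the mild anchor is worded as an absence requirement for this very parameter.

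Other points on that side stand:

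- Graders score from Appendix IV, not from the SAP. The SAP also omits the other parameters' definitions, so its silence on the exclusion adds little.
- Nothing here favours the active mask. Graders are blinded and the same rules apply in both arms, so the effect is attenuation.
- The 3/4 boundary lies inside the 1-6 entry range, so the split at that boundary does not change eligibility. A face even in tone apart from lentigines could in principle be scored 0 on the definition and 4 on the anchors, but the documents give no idea how often that arises.
- In the title and objective, mottled hyperpigmentation describes the population. The decision rule in SAP section 6.2 does not use it.

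On concealment, the Protocol synopsis says that secondary variables are analysed in the same way as the primary, which could be read as including per-grader analyses. SAP section 6.4.2 is more specific and says average scores. The SAP does plan listings of the scale data, but no planned analysis would look for a split.

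**Conclusion.** The definition and the anchors contradict each other on lentigines, and the visible text does not settle which governs. The consequence is conditional: on faces with persisting lentigines, graders who follow the anchors cannot go below 4, while graders who follow the definition can.

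A reader might infer that real improvement can never register below 4. The documents do not support that. Faces without lentigines have no such floor, nor do graders who apply the exclusion, and improvement within 4-6 still registers in half points.

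Nor should the figures 0.85, 0.69 and 0.54 be read as the expected result. They describe a single anchor-following grader, and apply to the averaged endpoint only if all three graders set the exclusion aside. In that case there is no split between graders. With a split, the illustration gives 0.95 to 0.85 with one such grader and 0.90 to 0.69 with two. The baseline spread, the fall of 1.0, the lentigo shares and the floor rule are all assumptions; none comes from the documents.

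This is a wording conflict with a possible attenuating effect on one secondary endpoint. The primary endpoint is untouched.

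**What to change.** Add one sentence to Appendix IV and to SAP section 4 stating that, consistent with the definition, the presence or absence of lentigines is disregarded when the mottled hyperpigmentation anchors are applied. Give all three graders that single written rule before grading starts, which means before the first Visit 1, since the principal investigator scores this parameter for entry.

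A clarifying sentence is preferable to deleting the lentigines wording, because it leaves the printed scale intact. The cost is a short amendment and a grader briefing. The small downside is slightly less comparability with the anchors as printed. It is best done in advance: once scores have been given under mixed rules, they would show disagreement between graders but not which rule produced it.

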**Modified Griffiths Scale:**

Rating (Score)	Category	Description
0	None	See below for parameter-specific descriptions.
1-3	Mild	
4-6	Moderate	
7-9	Severe	

**Surface Roughness (using Modified Griffiths Scale):**

Rating (Score)	Category	Description
0	None	Skin perfectly smooth.
1-3	Mild	Slight laxity of skin. Some surface roughness visible.
4-6	Moderate	Tactile and/or visible roughness demonstrable.
7-9	Severe	Topography of skin (visible and tactile) is undulating and rough.

**Uneven Skin Tone (using Modified Griffiths Scale):**

Rating (Score)	Category	Description
0	None	Uniform natural skin color; perfect evenness.
1-3	Mild	“Barely” to “slightly” to “slightly to mildly”...perceivable areas of redness, yellowness, or darkness.
4-6	Moderate	“Mildly to moderately” to “moderately” to “pronounced”...perceivable areas of redness, yellowness, or darkness
7-9	Severe	“Pronounced” to “pronounced to significantly” to pronounced (severe)”... perceivable areas of redness, yellowness, or darkness

**Mottled Hyperpigmentation (using Modified Griffiths Scale):**

[figure not shown]
Rating (Score)	Category	Description
0	None	Perfectly even in tone (no redness or hyperpigmentation).
1-3	Mild	Early color variation; no lentigines (freckles may be present).
4-6	Moderate	Early to moderate dyspigmentation/telangiectasia may be present; one or more lentigines.
7-9	Severe	Dyschromia (mottled and/or discrete) is likely, or it may be replaced by quite definite yellowing.

**Sallowness or Yellowing (using Modified Griffiths Scale):**

Rating (Score)	Category	Description
0	None	No evidence of yellowing; depending on Fitzpatrick skin type, the skin may be very pink and rosy.
1-3	Mild	No yellowing; depending on Fitzpatrick skin type, the skin may be pink and rosy to slightly pink and rosy.
4-6	Moderate	Early evidence of yellowing; one or more lentigines; depending on Fitzpatrick skin type, the skin may be slightly pink and rosy to sallow and pale.
7-9	Severe	Quite definite yellowing. Depending on Fitzpatrick skin type, the skin may be sallow and pale to very sallow and pale.

**Lack of Radiance (using Modified Griffiths Scale):**

Rating (Score)	Category	Description
0	None	Extremely bright, clear, radiant
1-3	Mild	“Very” to “mildly” to “mildly to moderately”...bright, clear, radiant
4-6	Moderate	Moderately bright, clear, radiant skin, but with some matte appearance to mildly dull/matte appearance to moderately dull/matte appearance.
7-9	Severe	“Moderately to pronounced” to “pronounced” to “significantly (severe)” dull/matte appearance

Protocol Title: A Randomized, Evaluator-Blinded Clinical Study to Evaluate the Efficacy and Tolerability of an Investigational Light Therapy Mask on Subjects with Mild to Moderate Mottled Hyperpigmentation and Moderate to Severe Facial Wrinkles

Protocol Identification: CO-1705 1113 2943-SACT

Version & Date: Draft Version 2.0, 26 September 2017

■ [REDACTED]

[figure not shown]
■ [REDACTED]

[REDACTED]

[figure not shown]
Protocol Title: A Randomized, Evaluator-Blinded Clinical Study to Evaluate the Efficacy and Tolerability of an Investigational Light Therapy Mask on Subjects with Mild to Moderate Mottled Hyperpigmentation and Moderate to Severe Facial Wrinkles

Protocol Identification: CO-1705 1113 2943-SACT

Version & Date: Draft Version 2.0, 26 September 2017

## Appendix VI. Subject Instructions – Prior to Treatment Period

### Subject Instructions – Prior to Treatment Period Protocol # CO-1705 1113 2943-SACT; Site Study # 8376

You have been provided with an **AM & PM Cleanser** and an **AM Moisturizer (with SPF 30)**. Please use them as follows:

- Wash your face twice daily (morning and evening) with the **AM & PM Cleanser**. In the morning after washing, apply the **AM Moisturizer** full-face. In the evening after washing, you may apply the **AM Moisturizer** again, if desired. See the detailed instructions below.

#### In the morning:

1. Wash your face with the **AM & PM Cleanser**:  
*Wet your face. Pump cleanser into your hands, add water, and work into a lather. Massage your face gently and rinse thoroughly. Pat dry.*
2. Apply the **AM Moisturizer** full-face:  
*Apply liberally over your entire face in gentle massaging strokes until fully absorbed. After product dries, you may apply your makeup as usual.*

#### In the evening:

1. Wash your face with the **AM & PM Cleanser**:  
*Wet your face. Pump cleanser into your hands, add water, and work into a lather. Massage your face gently and rinse thoroughly. Pat dry.*
2. If desired, you may apply the **AM Moisturizer** again after washing and drying your face.

#### Other Instructions:

- During the study, do not use any facial cleansers, moisturizers, sunscreens, or light-based devices other than those provided for this study.
- Do not use any exfoliating, sunless tanning, skin lightening, skin firming, or anti-aging products on your face during the study.
- Do not receive any professional or aesthetic facial spa procedures during the study.
- Continue using your regular brands of color cosmetics (i.e. makeup) and makeup remover during the study. Do not start using any new skincare products or change your currently used brands during the study. Use only facial products reviewed by study staff at Visit 1.

-- Continued on Back --

- On the day of study visits: remove all leave-on facial products (including eye makeup) and wash with the provided facial cleanser prior to the visit and then do not apply any leave-on facial products until the visit is completed. Note: if you do not follow these directions, you will be asked to remove your makeup/products and wash your face with the provided cleanser on-site prior to the acclimation period.
- Avoid extended periods of sun exposure and all use of tanning beds for the duration of the study. Extra care should be taken to avoid sun exposure from 11 AM to 4 PM.
- Maintain your birth control method for the duration of the study and 30 days after completion.
- If you are using a hormone replacement therapy (HRT), do not change it during the study. If you are not using a HRT, do not begin one during the study.
- Attend all scheduled visits.
- Do not begin any other clinical study during the current study.
- Report any side effects, changes in health/medication, pregnancies, issues, or questions to the study staff.
- Bring your study products to all visits. All products must be returned when requested by the Study Site.

